9.5.1.5.3 STUDY-SPECIFIC ADVERSE EVENTS

Not applicable.

9.5.1.5.4 LABORATORY MEASUREMENTS

Clinical laboratory tests to be performed, including hematology, chemistry, and urinalysis, are summarized in [Table 5](#). Subjects should be in a seated or supine position during blood collection. The Schedule of Procedures/Assessments ([Table 6](#)) shows the visits and time points at which blood for clinical laboratory tests and urine for urinalysis will be collected in the study.

Table 5 Clinical Laboratory Tests

Category	Parameters
Hematology	Hematocrit, hemoglobin, platelets, RBC count, and WBC count with differential (bands, basophils, eosinophils, lymphocytes, monocytes, neutrophils)
Coagulation ^a	INR derived from the prothrombin time, PTT
Chemistry	
Electrolytes	Chloride, potassium, sodium
Liver function tests	Alanine aminotransferase, alkaline phosphatase, aspartate aminotransferase, gamma glutamyl transpeptidase, direct bilirubin, total bilirubin
Renal function tests	Blood urea/blood urea nitrogen, creatinine
Other	Albumin, calcium, cholesterol, globulin, glucose, lactate dehydrogenase, phosphorus, TFT ^b (TSH, free triiodothyronine, and free thyroxine), vitamin B12 ^b , total protein, triglycerides, uric acid
Urinalysis	Bacteria, casts, crystals, epithelial cells, glucose, ketones, occult blood, pH, protein, RBCs, specific gravity, WBCs

INR = international normalized ratio, PTT = partial thromboplastin time, RBC = red blood cell, TFT = thyroid function test, TSH = thyroid stimulating hormone, WBC = white blood cell.

a: In subjects who participate in the CSF substudy, a clotting screen (PTT and INR derived from the prothrombin time) will be performed.

b: Screening only.

Clinical laboratory tests during the study will be performed by a central laboratory. All blood and urine samples will be collected and sent to the central laboratory on the day of collection unless otherwise instructed. In cases of a safety concern, blood samples will be split (or 2 samples drawn) to allow a local laboratory analysis in addition to the central laboratory. Laboratory certification as available will be included in the final clinical study report for this study.

A laboratory abnormality may meet the criteria to qualify as an AE as described in this protocol (see [Section 9.5.1.5.1](#) and the eCRF Completion Guidelines. In these instances, the AE corresponding to the laboratory abnormality will be recorded on the AE eCRF.

9.5.1.5.5 VITAL SIGNS, HEIGHT AND WEIGHT MEASUREMENTS

Vital sign measurements (ie, SBP and DBP [mmHg] including orthostatic evaluations, pulse [beats per minute], respiratory rate [per minute], body temperature [in centigrade]), height (m), and weight (kg) will be obtained at the visits designated in the Schedule of Procedures/Assessments ([Table 6](#)) by a validated method. Blood pressure and pulse will be measured after the subject has been resting for 10 minutes in the supine position. Blood pressure and pulse will be measured again after standing up for 2 minutes. All BP measurements should be performed on the same arm, preferably by the same person. (revised per Amendment 01)

When vital signs are to be obtained concurrently with PK or other blood samples, the vital sign measurements will be performed prior to drawing blood samples in order to maximize the accuracy of blood sampling times while minimizing the potential effects of blood drawing on recordings obtained during safety assessments.

Orthostatic (postural) hypotension will be defined as either asymptomatic orthostatic hypotension (change in blood pressure upon standing without lightheadedness) or symptomatic orthostatic hypotension (change in blood pressure upon standing accompanied by lightheadedness).

Orthostatic hypotension will be recorded based on the following criteria:

- Drop in systolic BP ≥ 20 mmHg, or
Drop in diastolic BP ≥ 10 mmHg (revised per Amendment 01)

Occurrences of orthostatic hypotension as defined above that also meet any of the following criteria are considered clinically significant and will be reported as AEs in this study:

- Postural lightheadedness noted upon standing (ie, symptomatic orthostatic hypotension)
- Requires intervention (eg, resumption of recumbent position, IV fluids, etc.)

Postural lightheadedness upon standing if accompanied by orthostatic BP changes meeting the above criteria of orthostatic hypotension should be reported as AE of orthostatic hypotension. (revised per Amendment 01)

9.5.1.5.6 PHYSICAL EXAMINATIONS

Complete and brief physical examinations will be performed as designated in the Schedule of Procedures/Assessments (Table 6). A complete physical examination will include evaluations of the head, eyes, ears, nose, throat, neck, chest (including heart and lungs), abdomen, limbs, a dermatologic exam, and a neurologic examination (including general status, cranial nerve function, motor system, coordination/cerebellar function, reflexes, and sensory system). A urogenital examination will only be required in the presence of clinical symptoms related to this region. Documentation of the physical examinations will be included in the source documentation at the site. Significant findings at the Screening Visit will be recorded on the Medical History and Current Medical Conditions eCRF. Only changes from screening physical examination findings that meet the definition of an AE will be recorded on the AE eCRF.

9.5.1.5.7 ELECTROCARDIOGRAMS

Electrocardiograms will be obtained as designated in the Schedule of Procedures/Assessments (Table 6). Triplicate ECG will be performed after subject has been resting in the supine position for at least 10 minutes. The mean QTcF and other ECG intervals will be determined. An ECG abnormality may meet the criteria of an AE as described in this protocol (see

[Section 9.5.1.5.1](#)) and the eCRF Completion Guidelines. In these instances, the AE corresponding to the ECG abnormality will be recorded on the Adverse Events eCRF.

9.5.1.5.8 OTHER SAFETY ASSESSMENTS

Columbia Suicide Severity Rating Scale (C-SSRS)

An assessment of suicidality using the C-SSRS will be performed as designated in the Schedule of Procedures/Assessments ([Table 6](#)).

Movement Disorders Society Unified Parkinson's Disease Rating Scale (MDS UPDRS) Part III: Motor Examination

The MDS UPDRS scale evaluates extrapyramidal features in motor function in Parkinson's disease. It contains 33 items in 18 categories: (1) speech, (2) facial expression, (3) rigidity, (4) finger tapping, (5) hand movements, (6) supinational and pronation movements of hands, (7) toe tapping, (8) leg agility, (9) arising from chair, (10) gait, (11) freezing of gait, (12) postural stability, (13) posture, (14) body bradykinesia, (15) postural tremor of hands, (16) kinetic tremor of hands, (17) rest tremor amplitude and (18) constancy of rest tremor. Each item is scored 0 to 4, giving a total score range 0 to 132. As far as is practical, the motor assessments should be made with the subject in the "on" state at each visit and at the same time relative to the subject's last dose of Parkinson's disease medication (such as L-dopa). (revised per Amendment 01)

9.5.1.6 Other Assessments

9.5.1.6.1 DEMENTIA-RELATED QUALITY OF LIFE AS ASSESSED BY THE DEMENTIA QUALITY OF LIFE MEASURE (DEMQOL; INTERVIEW OF SUBJECT) AND DEMENTIA QUALITY OF LIFE MEASURE BY PROXY (DEMQOL-PROXY; INTERVIEW OF CAREGIVER ABOUT SUBJECT)

The DEMQOL and DEMQOL-Proxy are appropriate for use in subjects with mild-moderate dementia (MMSE ≥ 10). The DEMQOL is a 28-item scale and DEMQOL-Proxy is a 31-item scale. Both are interview administered. There are 5 domains: daily activities, health and well-being, cognitive functioning, social relationships and self-concept. All items are given a score from 1 to 4 and summed to produce domain scores. A general quality of life item is unscored. The DEMQOL and DEMQOL-Proxy will be assessed at Baseline (Visit 2) and Day 84 (Visit 8). Should the subject progress to severe dementia during the course of the study, only the DEMQOL-Proxy should be administered.

9.5.1.6.2 GENERAL HEALTH STATUS AS ASSESSED BY THE EUROQOL- 5 DIMENSION QUESTIONNAIRE (EQ-5D; COMPLETED BY SUBJECT) AND EUROQOL- 5 DIMENSIONS QUESTIONNAIRE BY PROXY VERSION 1 (EQ-5D PROXY; CAREGIVER COMPLETION OF REPORT ABOUT SUBJECT)

The EQ-5D is a widely used general health state and health utility scale to assess the impact of any health intervention on the general quality of life of patients. The health utility values are utilized as weights to life expectancy estimates and ultimately are used in a metric known as

an incremental cost effectiveness ratio (ICERs). ICERs are used by health authorities to make key decisions that ultimately impact the relative funding of health interventions across multiple therapeutic areas based on their relative cost-effectiveness. Thus, the EQ-5D is not specifically developed for any particular disease to allow this cross-therapeutic comparison.

The scale consists of 5 specific questions (regarding mobility [walking], self-care [washing and dressing], usual activities, pain/discomfort, and anxiety/depression) and 1 overall health rating. The EQ-5D is selected in this study due to its brevity and content. The EQ-5D-5L (5 levels of responses to each of the 5 questions) will be utilized in this study as it allows for a more granular assessment of the impact of intervention.

The proxy EQ-5D version is available as EQ-5D-5L (5 levels of responses to each of the 5 questions) and will be utilized to assess the caregiver's or informant's perspective of the subject's health. The proxy EQ-5D-5L is available in 2 versions: Proxy version 1 where the caregiver or informant (the proxy) is asked to rate the patient's health-related quality of life in their (the proxy's) opinion and Proxy version 2 where the caregiver or informant (the proxy) is asked to rate how he/she (the proxy) thinks the subject would rate his/her own health-related quality of life, if the subject were able to communicate it. Only Proxy version 1 will be utilized in this particular study. The EQ-5D and EQ-5D-Proxy will be assessed at Baseline (Visit 2) and Day 84 (Visit 8).

9.5.2 Schedule of Procedures/Assessments

9.5.2.1 Schedule of Procedures/Assessments

[Table 6](#) presents the schedule of procedures/assessments for the study.

Table 6 Schedule of Procedures/Assessments in Study E2027-G000-201

Phase Period	Prerandomization		Randomization							Early Discontinuation (ED) ^d	Unscheduled ^e
	Screening	Baseline	Treatment					Follow-Up			
Visit ^a	1 ^b	2 ^c	3 ^c Telephone	4	5	6	7	8	9		
Day	-42 to -8	-7 to -1	1	14	28	42	63	84	112		
Weeks elapsed since randomization			0	2	4	6	9	12	16		
Assessments											
Informed consent	X										
Informed consent for CSF substudy (optional)	X										
Inclusion and exclusion criteria	X	X									
Demographics	X (Tier 1)										
Medical history	X (Tier 1)										
History of DLB	X (Tier 1)										
Prior and concomitant medications	X (Tier 1)	X	X	X	X	X	X	X	X	X	X
MMSE ^{f,g}	X (Tier 2)							X	X	X	X
GDS ^f	X (Tier 2)										
MoCA ^{f,g}	X (Tier 2)	X				X		X	X	X	X
SCOPA-Sleep ^{f,g}	X (Tier 2)	X				X		X	X	X	X
SFQ ^f	X (Tier 2)										
CFI ^{f,g}	X (Tier 2)	X				X		X	X	X	X
NPI ^{f,g}	X (Tier 2)	X				X		X	X	X	X
CIBIS-Plus ^g		X									

Table 6 Schedule of Procedures/Assessments in Study E2027-G000-201

Phase Period	Prerandomization		Randomization							Early Discontinuation (ED) ^d	Unscheduled ^e
	Screening	Baseline	Treatment					Follow-Up			
Visit ^a	1 ^b	2 ^c	3 ^c Telephone	4	5	6	7	8	9		
Day	-42 to -8	-7 to -1	1	14	28	42	63	84	112		
Weeks elapsed since randomization			0	2	4	6	9	12	16		
Assessments											
CIBIC-Plus ^g						X		X		X	X
CGIC-DLB						X		X		X	X
DEMQOL-Proxy		X						X			
DEMQOL		X						X			
EQ-5D		X						X			
EQ-5D Proxy		X						X			
Modified Hachinski Ischemic Scale	X (Tier 3)										
UPDRS-III	X (Tier 3)							X	X	X	X
HYS	X (Tier 3)										
C-SSRS	X (Tier 3)	X		X	X	X	X	X	X	X	X
Height	X (Tier 4)										
Weight	X (Tier 4)							X		X	X
Vital signs ^h	X (Tier 4)	X		X	X	X	X	X	X	X	X
Complete physical examination	X (Tier 4)										
Brief physical examination		X						X	X	X	X
12-lead ECG ⁱ	X (Tier 4)	X		X	X	X	X	X	X	X	X
Blood and urine for clinical laboratory tests ^j	X (Tier 4)	X ^j				X		X		X	X

Table 6 Schedule of Procedures/Assessments in Study E2027-G000-201

Phase Period	Prerandomization		Randomization							Early Discontinuation (ED) ^d	Unscheduled ^e
	Screening	Baseline	Treatment					Follow-Up			
Visit ^a	1 ^b	2 ^c	3 ^c Telephone	4	5	6	7	8	9		
Day	-42 to -8	-7 to -1	1	14	28	42	63	84	112		
Weeks elapsed since randomization			0	2	4	6	9	12	16		
Assessments											
Blood for vitamin B12 test	X (Tier 4)										
Blood for thyroid function tests ^k	X (Tier 4)										
Urine drug screen	X (Tier 4)	X									X
Serum pregnancy test ^l	X (Tier 4)										
Urine pregnancy test ^l		X									
Safety brain MRI ^m	X (Tier 5)										X ^m
DAT brain imaging, MIBG scan ⁿ	X (Tier 6)										
CSF sample by LP for PK and PD biomarkers ^o	X						X				
Plasma sample for PK ^p				X		X	X	X		X	X
PGx sample ^q		X									
Adverse events	X	X	X	X	X	X	X	X	X	X	X
Randomization ^c		X									
Dispense study drug		X		X	X	X	X				

CFI = Cognitive Fluctuation Inventory, CGIC-DLB = Clinician Global Impression of Change - in Dementia with Lewy Bodies, CIBIC-Plus = Clinician’s Interview Based Impression of Change Plus Caregiver Input, CIBIS-Plus = Clinician Interview Based Impression of Severity plus Caregiver Input, CSF = cerebrospinal fluid, C-SSRS = Columbia Suicide Severity Rating Scale, DAT = dopamine transporter, DEMQOL = Dementia Quality of Life, DLB = dementia with Lewy bodies, ECG = electrocardiogram, ED = early discontinuation, EQ-5D = EuroQol Five Dimensions Questionnaire, GDS = Geriatric Depression Scale, HYS = Hoehn and Yahr Scale, LP = lumbar puncture, MIBG = [(123)I]-metaiodobenzylguanidine, MMSE = Mini-Mental State Examination, MoCA = Montreal Cognitive Assessment, MRI = magnetic resonance imaging, NPI = Neuropsychiatric Inventory, PD = pharmacodynamic, PGx = pharmacogenomic, PK = pharmacokinetic, SCOPA-Sleep = Scales for Outcome in Parkinson’s disease-Sleep, SFQ = Short Fluctuation Questionnaire, UPDRS-III = Unified Parkinson’s Disease Rating Scale Part III.

a: A window of ±3 days will be permitted for Visit 4 to 9 (Follow-Up) inclusive.

- b: The Screening Visit takes place over a period of up to 5 weeks. Subjects who complete screening assessments in less than 5 weeks may proceed to the Baseline Period. At Screening, assessments are grouped into tiers and should be performed sequentially. Subjects will need to satisfy the eligibility criteria in each tier before proceeding to the next tier. Subjects who cannot complete screening within 5 weeks should be discussed with the sponsor for extension of the Screening Period by up to 2 weeks.
- c: Visit 2 is the Baseline Visit and may be conducted up to 1 week before the first dose of study drug (ie, from Day -7 to Day -1). The Baseline Visit should be at least 2 weeks after the day of Screening Visit Tier 2 assessments. After completion of study assessments subjects who are eligible will be randomized to placebo or E2027. They will be dispensed with study drug before leaving clinic at Visit 2. Visit 3 (Day 1) will be conducted by telephone. On Day 1 the subject will start taking study drug in the morning at home. The site study staff will telephone the subject/caregiver to check that the subject has taken study drug and to elicit any AEs. Subjects who develop acute illnesses which make it inappropriate to start taking study drug may have their Baseline Period extended by 1 week after discussion with the sponsor medical monitor.
- d: Subjects who discontinue study drug prematurely for any reason will undergo an Early Discontinuation (ED) Visit within 7 days of their final dose of study drug. In addition, subjects who prematurely discontinue study drug are expected to continue in the study for the originally scheduled visits, starting with next such visit that is >7 days after the ED Visit. Subjects who prematurely discontinue the study should attend at least 1 originally scheduled visit after the ED Visit.
- e: Unscheduled visits may be conducted at any time as clinically indicated in the judgment of the investigator or as specified in the protocol. Not all assessments indicated under Unscheduled Visits need to be conducted – actual assessments needed will be determined by the investigator or as specified in the protocol and will be based on the specific visit.
- f: At Screening, Tier 2 assessments in subjects should be performed in the following order: MMSE and GDS first; then MoCA and SCOPA-Sleep. The caregivers or informants should complete the SFQ, CFI and NPI. Subjects who do not meet eligibility criteria on MMSE or GDS should be screen failed and the other assessments do not need to be performed. The caregiver or informant must attend in person with the subject. The above assessments should be completed before more invasive procedures (eg, physical examination, ECG, blood draws). Assessments at all other tiers are not required to be performed in any prespecified order.
- g: At Visits 2, 6, 8, ED Visit and FU Visit, study assessments should be conducted at approximately the same time of the day whenever possible (preferably in the morning). The MoCA should be administered first. It is recommended that after the MoCA the following efficacy assessments in subjects should be performed in the following overall order (other study assessments may be conducted in between these efficacy assessments): CIBIS/CIBIC-Plus, MMSE (Visit 8 only) and SCOPA-Sleep. The caregiver or informant will also complete the CIBIS/C-Plus, NPI and CFI. The caregiver or informant must attend in person with the subject. The CIBIS-Plus and CIBIC-Plus should be performed by an independent rater from other scales. As far as possible efficacy assessments should be completed before more invasive procedures (eg, physical examination, ECG, blood draws) unless otherwise specified. At Visits 6, 8 and ED Visit the MoCA should be the first clinical scale to be administered postdose and before the first postdose PK sample. At Visits 6, 8 and ED Visit the investigator should complete the CGIC-DLB after reviewing all the subject's efficacy endpoints.
- h: Single measurements of vital signs will be performed after subject has been resting supine for at least 10 minutes. Vital signs include temperature, respiratory rate, supine blood pressure and pulse. Blood pressure and pulse will be measured again after standing up for 2 min. At Week 2 (Visit 4), Week 6 (Visit 6) and Week 12 (Visit 8) (or ED Visit) vital signs will be taken at 1 – 3 hours postdose, before PK sampling. At Week 9 (Visit 7) vital signs will be taken at 1 – 4 hours postdose, before PK sampling. (revised per Amendment 01)
- i: Triplicate ECG will be performed after subject has been resting supine for at least 10 min. The mean QTcF and other ECG intervals will be determined.
- j: Clinical laboratory tests consist of hematology (complete blood count), clinical chemistry and urinalysis. In subjects who participate in the CSF substudy, clotting screen (PT, APTT, and INR) will also be performed only at the Screening Visit after eligibility has been established and consent for CSF has been given, but before the LP.
- k: Thyroid function tests include thyroid stimulating hormone, free triiodothyronine, and free thyroxine.
- l: Female subjects who are <60 years of age and not surgically sterilized.
- m: Safety MRI of the brain will be acquired using a standardized procedure that will include gradient echo, long tau inversion recovery, and diffusion-weighted imaging sequence images at screening. MRI of the brain will be read by an approved central reader. Safety MRI of the brain may be performed at Unscheduled Visits if deemed appropriate by the investigator, but is not required for all Unscheduled Visits. Subjects who are rescreened do not need to have a new MRI at rescreening if there was an MRI within 90 days before rescreening that did not have exclusionary characteristics.
- n: DAT brain imaging scan or myocardial MIBG scan will be performed by the local hospital radiology department in accordance with local procedures and must be performed at least 7 full days prior to Baseline. The rules regarding when DAT brain imaging or MIBG scan will be performed are specified in Inclusion Criterion 2.

-
- o: CSF will be collected by LP in subjects who participate in the CSF substudy. During Screening CSF may be collected at any time after completion of screening procedures and a subject is deemed eligible at least 1 week before Visit 2; if necessary in these subjects the Screening Period may be extended by 1 week after discussion with the sponsor medical monitor. CSF will be collected again at Visit 7. CSF will be collected in the morning at approximately the same time, either fasted (preferred) or at least 2 h after breakfast. The timing of the Screening CSF collection needs to be scheduled carefully such that subsequent collection (at Visit 7) can be performed at a similar time of day (± 2 hours) for each individual subject. A gravity drip collection method must be used. Subjects will be encouraged to stay at the site after completion of LP for medical observation. If the LP and cognitive tests are performed on the same day, the LP must be performed after the cognitive tests are completed. At Visit 7, a predose blood sample for PK will be taken first, followed by LP. Subjects will then be dosed with study drug and a PK sample will be collected at 1 – 4 hours postdose. If Visit 7 occurs after an ED Visit, blood PK samples and CSF will not be collected.
- p: The day before the visits at which PK sampling will be done, the site study team will phone the subject and caregiver/informant to remind the subject not to take the study drug in the morning of the visit on the next day. In the morning of the day of the visit, the subjects should take breakfast at home as normal if applicable. Thereafter a predose PK sample will be taken in clinic. Study drug will be administered and 1 postdose PK sample will be taken: 1 - 3 hours postdose at Week 2 (Visit 4). Study drug will be administered and 2 postdose PK samples will be taken: 1 - 3 hours postdose and 4 - 8 hours postdose at Week 6 (Visit 6) and Week 12 (Visit 8) (or ED Visit). At Week 6 (Visit 6) and Week 12 (Visit 8) (or ED Visit) study drug will be administered before efficacy assessments are performed. Study drug will be administered and 1 postdose PK sample will be taken 1 - 4 hours postdose at Week 9 (Visit 7). In subjects who participate in the CSF substudy a predose PK sample will be collected at Week 9 (Visit 7), followed by CSF collection. The subject will then be dosed with study drug and a PK sample will be collected at 1 - 4 h postdose. In addition, subjects or their caregivers/informants will need to record the time of dosing of study drug at home for 2 days before these visits. If these visits take place after the ED Visit, blood PK samples will not be collected.
- q: PGx participation is voluntary. For subjects who have provided separate informed consent to participate in the PGx assessment, a blood sample for genomic DNA will be collected at the Baseline Visit. If it cannot be collected at the designated time point, it may be collected at a time point after baseline.

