9.1.4 Follow-Up Period

After the Treatment Period, subjects will undertake a Follow-Up Visit 4 weeks after the final dose of study drug. Efficacy assessments should be performed at approximately the same time of the day as at the Baseline Visit whenever possible (preferably in the morning). The MoCA should be the first clinical scale to be administered before any invasive procedures. It is recommended that other efficacy assessments in subjects should be performed in the following overall order (other study assessments may be conducted in between these efficacy assessments): MMSE and SCOPA-Sleep. The caregiver or informant will also complete the CFI and NPI. Safety assessments will also be completed.

The end of study is defined as the last subject completing the Follow-Up Visit.

Subjects who prematurely discontinue study drug for any reason will undergo an Early Discontinuation (ED) Visit within 7 days of their last dose of study drug. The safety and efficacy assessments normally performed after 12 weeks of treatment will be conducted at the ED Visit. In addition, subjects who discontinue study drug are expected to continue in the study for the originally scheduled visits, starting with the next such visit that is >7 days after the ED Visit. Subjects who prematurely discontinue the study should attend at least 1 originally scheduled visit after the ED Visit.

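### Table 6 footnote p orders a dose at the Early Discontinuation Visit without limiting it to subjects still taking study drug

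*Protocol*

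**What the plan says.** **Dosing at the ED Visit.** Footnote p to Table 6 (Protocol 9.5.2.1) gives the instruction twice. With the PK sampling times for Week 6 and Week 12 (or ED Visit) it says "Study drug will be administered and 2 postdose PK samples will be taken". It then says "At Week 6 (Visit 6) and Week 12 (Visit 8) (or ED Visit) study drug will be administered before efficacy assessments are performed".

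**Timing of assessments.** Footnote g adds "At Visits 6, 8 and ED Visit the MoCA should be the first clinical scale to be administered postdose". Footnote h, after naming Weeks 2, 6 and 12, continues "or ED Visit) vital signs will be taken at 1 – 3 hours postdose, before PK sampling". Neither g nor h orders a dose, but both presuppose one.

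**Who attends.** Footnote d says "Subjects who discontinue study drug prematurely for any reason will undergo an Early Discontinuation (ED) Visit within 7 days of their final dose"; Section 9.1.4 agrees ("will undergo an Early Discontinuation (ED) Visit within 7 days of their last dose of study drug"). Section 9.5.5 also sends everyone who discontinues the study to the ED procedures in Table 6.

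**When drug must stop.** Sections 9.5.1.5.1 and 9.5.5 require permanent discontinuation of study drug for a bullous or a moderate-to-severe rash attributed to it. Section 9.5.5 requires discontinuation for mean QTcF above 500 ms. Sections 9.4.7.2 and 9.5.5 require it when a prohibited interacting medication is started. Section 9.4.7.3 requires it for male subjects who need contraception but cannot practise it.

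**The concern.** The ED Visit is defined by the subject having stopped study drug, yet the schedule orders study drug to be given there. A site that follows footnote p exactly would give one more dose to a subject already stopped, possibly for safety. A site that rightly withholds the dose has no instruction for the postdose windows in g, h and p. The issue is therefore mainly subject protection and consistent conduct at sites, and only secondarily the quality of the ED data.

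**Working it through.** The plan states no figure to reproduce on this point. The check is whether any sentence limits the ED dose to subjects still on drug, followed by the size per affected subject.

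**1. Search for a limiting sentence.**
- Footnotes p, g and h: no condition on treatment status.
- Footnotes o and p do contain exceptions, but for visits that take place *after* the ED Visit, and they withhold PK blood (and, in o, CSF), not doses.
- Section 9.5.1.4.1 describes clinic dosing for PK at Weeks 2, 6, 9 and 12 and does not mention the ED Visit.
- Section 9.4.5 tells subjects to hold the home dose on the morning of PK visits. It does not say who is dosed in clinic.
- The row of Table 6 for dispensing study drug has no mark under ED. It has none at Visit 8 either, where footnote p clearly intends a clinic dose, so the blank does not bar one.

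No limit was found.

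**2. Footnote p against the stop rules.** The rules for rash, QTcF, interacting medication and male contraception each end dosing, and footnote p excepts none of them. Subjects who stop by choice, or for an adverse event left to the investigator's judgement, also reach the ED Visit, and no drug-specific rule bars the extra dose for them.

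**3. Blood volume per affected subject.** Table 7 gives 10 PK samples × 6 mL = 60 mL, and the count agrees with the schedule: 2 (Week 2) + 3 (Week 6) + 2 (Week 9) + 3 (Week 12) = 10.
- As written at the ED Visit: 1 predose + 2 postdose = 3 draws; 3 × 6 = 18 mL, plus one dose (50 mg if on E2027).
- With no dose and a single sample: 1 × 6 = 6 mL. Difference: 18 − 6 = 12 mL.

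**4. Would the dose be a real re-exposure?** Section 7.1.1.2.1 gives a mean half-life of about 40 hours after 14 days of dosing in healthy subjects aged 50 to 85. Assuming simple first-order decline, the fraction left t hours after the last dose is 0.5^(t/40):

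| Days since last dose | t/40 | Fraction left |
|---|---|---|
| 1 | 24/40 = 0.6 | about 66% |
| 3 | 72/40 = 1.8 | about 29% |
| 7 | 168/40 = 4.2 | about 5% |

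A dose at a day-7 ED Visit would follow near washout. It would also become the last dose, restarting the 28-day treatment-emergent window (Protocol 9.7.1.8.2) and the 98-day contraception period (9.4.7.3).

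**5. How many subjects?** This cannot be derived. The planned 12% (182 − 160 = 22 subjects) is study dropout. It does not bound drug discontinuation, because "subjects who discontinue study drug are expected to continue in the study for the originally scheduled visits".

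**The case against.** The strongest reply is that the literal reading defeats itself. If a dose is given at the ED Visit, the earlier dose was not the final one. The reading that keeps footnotes d and p consistent is that clinic dosing applies only when the ED Visit falls on the last dosing day. The context supports this: footnote p has the site call the day before to "remind the subject not to take the study drug in the morning of the visit on the next day" and asks for home dosing times over the previous 2 days, and Section 9.4.5 tells subjects to hold the morning dose. Only a subject still dosing can do these things. Specific stop rules, and the right in Section 9.3.3 to stop at any time, would also prevail over a PK-timing footnote.

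Most of this stands as evidence of intent, and it makes an actual extra dose unlikely. It does not supply the missing rule. The same words serve the routine on-treatment visits, and the exceptions in o and p show that discontinued subjects were considered while ED dosing was left open.

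Two further objections have some force. The ED draws replace later PK draws, so even an ED Visit after Week 9 totals 2 + 3 + 2 + 3 = 10 draws, the 60 mL already planned; blood volume is a minor matter. And Section 7.1.1.2.2 reports a mean placebo-corrected QTcF change of only 0.71 ms (upper 90% limit 3.41 ms) at 50 mg exposure, on preliminary data from healthy subjects. That argues against a large hazard from one dose, but it does not justify re-dosing someone stopped for QTcF above 500 ms or a drug rash.

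**Conclusion.** The concern holds. Followed exactly, footnote p directs a further dose to subjects already off study drug, and it conflicts with the mandatory stop rules. This is a wrong instruction, not merely a missing detail, though it will probably seldom be acted on.

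The size is one extra dose and 12 mL of avoidable sampling per affected subject, in an unknown number of subjects. Subjects still taking drug on the day of the ED Visit, and not being stopped for safety or a prohibited medication, are unaffected.

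The data remain usable if the dose is withheld. Footnote g also sets time of day and MoCA-first order without reference to dosing, and the population PK model uses dosing history (Protocol 9.7.1.7.1). Any effect on the co-primary analyses is probably small, because the treatment effect targeted in SAP 5.4.1 applies whether or not treatment was discontinued. The re-exposure figures rest on the healthy-subject half-life carrying over to DLB subjects.

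**What to change.** Amend footnote p so that dosing and postdose PK samples at the ED Visit apply only if the subject is still taking study drug that day and is not being stopped for safety or a prohibited medication. Make the postdose timing in g and h conditional in the same way. For all other subjects at the ED Visit:

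- give no dose;
- take one PK sample and record the date and time of the last dose;
- do the MoCA first, at the usual time of day;
- take vital signs without dose timing.

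There is precedent: Section 9.5.1.5.1 already asks for a PK sample when drug is held for a suspected drug rash. The single sample is one reasonable choice; the condition on dosing is the essential part.

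The cost is one clause in p and matching words in g and h at the next protocol amendment, with no change to sample size or analysis. The downside is fewer dose-timed PK and vital-sign data at ED Visits.
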